Individuals may be apprehensive of utilizing their beliefs about CVD risk because they lack confidence in the accuracy of those beliefs. Their beliefs are ambiguous. If individuals are ambiguity seeking in the loss domain, which is often found (Dimmock et al 2015), and are informed that their risks are lower than they had reported, then on gaining confidence in their downwardly revised beliefs they may become responsive to them. Being surer that the CVD risk is 15% rather than being very uncertain that it is 20% may cause an individual to adopt healthier behaviour.

Test:

• Repeat the regressions of the previous test but rather than including a single indicator of treatment group enter two indicators. One identifies respondents in the treatment group informed that their risk is above their initially reported risk. The other identifies respondents in the treatment group informed that their risk is at or below their reported risk. If it is only the correction of bias in risk perceptions that affects behaviour, then only the first group should adopt healthier behaviour. The second group, if anything, should adopt less healthy behaviour. If, to the contrary, the second group responds to the positive news they are given of their CVD risk by adopting healthier habits, this suggests an effect through reduced ambiguity. In addition, we will examine how the provision of information affects stated confidence in individuals' estimates of their risks of heart attack/stroke.

Q6: Is PhilPEN effective in delivering primary prevention of CVD to those who seek care at RHU/CHCs?

[H6a] As currently implemented, PhilPEN does not reduce the risk factor exposure and increase the medication of individuals with elevated CVD risk.

Test:

- Induce random variation in presentation for checkup at RHU/CHCs, which under PhilPEN are required to conduct CVD risk assessment of all patients, to screen those meeting specified criterion, to counsel all those screened on smoking cessation and to provide hypertension and diabetes medication to those at high risk defined by the WHO PEN protocol.
- The information intervention will not be used to generate this random variation since beliefs about CVD risk can impact on behaviour directly even without contact with health facilities and the PhilPEN program.

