- Rather, a *randomized encouragement design* is adopted in which respondents in randomly selected barangays will be offered the opportunity to enter a lottery for a money prize on condition of attending a RHU/CHC for a checkup within a month. The lottery will have a selection probability of 10% and a prize of 5,000 PHP. There will be one lottery within each of the selected barangays.

- The offer of a lottery ticket will be used to instrument presentation for checkup at RHU/CHC allowing the effect of the latter on predicted 10-year CVD risk, plus risk factors (smoking, BMI, blood pressure), hypertension diagnosis and medication at follow-up to be identified.
- Specifically, we will estimate the regression model,

$$Y_{it} = \gamma Y_{it-1} + \beta x_{it-1} + \tau \,\hat{s_i} + \mu_{it} \tag{6.1}$$

where Y_{it} represents the outcome variable (e.g. predicted CVD risk) at follow-up and \hat{s}_i is the predicted value of a binary variable that equals one for those who attended a RHU/CHC for a checkup, and zero otherwise. The prediction is obtained from the first stage regression described in [H6b] that makes use of the random offer of entry to the lottery. Y_{it-1} and x_{it-1} are the outcome and covariates respectively at baseline. Note that only individuals that are either in the lottery incentive group or in the control group are used for this regression.

• The instrumental variable estimate of τ is an estimate of the impact of a RHU/CHC checkup on the outcome for those induced to present for checkup by the lottery offer who would not have presented for a checkup otherwise.

[H6b] The lottery offer is a strong instrument for presentation at a RHU/CHC for a checkup.

Test:

• Using both the treated respondents who are offered the lottery prize and the control respondents who are not, we will regress a binary variable indicating RHU/CHC attendance (s_i) on a binary variable indicating whether or not the lottery prize was offered (L_i) , i.e.

$$s_i = \gamma Y_{it-1} + \beta x_{it-1} + \kappa L_i + u_i.$$
(6.2)

 $\hat{\kappa} > 0$ indicates that the lottery offer raises attendance. We will test for weakness of the instrument.

[H6c] Individuals who have a preference for risk respond more to the offer of a lottery prize. Thus, the intervention has a larger effect on individuals who potentially engage most in lifestyles that bring exposure to CVD risk.

Elaboration

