improves implementation of the PhilPEN protocol across the board. Another is that the facility expends more effort on the patients entitled to enter the lottery, since it knows they are being monitored by the study, and neglects other patients. We will make efforts to avoid these reactions by encouraging the RHU/CHC to operate as it was and simply to issue the lottery tickets on completing a physical assessment of a patient presenting with a voucher. But even if the experimental effect cannot be completely avoided, it is not a major problem for the study. The lottery is used to provide random variation in go for a checkup at a RHU/CHC. This variation will be used to compare outcomes of those in the treatment group who go for a checkup with those in the control area who do not. We are not comparing outcomes of those who go for a checkup in the treatment and control barangays. So, even if the service improves for those in the control barangay, it does not invalidate our identification strategy.

11.Survey instrument

The baseline instrument contains a screening module to establish eligibility of the household and a main respondent for the study and interventions according to the inclusion/exclusion criteria described in section 9. Thereafter, two modules completed by the head of household, their spouse or another adult obtain information on housing conditions and ownership of assets that will be used to construct a wealth index. The randomly selected main respondent aged 40-70 will complete modules on socio-demographic characteristics, medical history, knowledge of CVD risk factors, health behaviour, CVD risk perceptions, general health (SF-36), health care utilization and expenses, work and earnings, and risk and time preferences.

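### The shared-facility defence of the lottery analysis rests on a contrast that models 6.1 and 6.2 do not use, and gives no identification argument for extra care to voucher holders

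*Combined protocol and SAP*

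**What the plan says.** Section 10.2 recognises that one RHU/CHC may serve both lottery and control barangays, and names two possible facility reactions. Care may improve for everyone, or "the facility expends more effort on the patients entitled to enter the lottery, since it knows they are being monitored by the study", at the expense of other patients. It plans to ask facilities to carry on as before and "simply to issue the lottery tickets on completing a physical assessment of a patient presenting with a voucher". It then argues that a remaining reaction is not a major problem, because the attendance difference that the offer induces serves to "compare outcomes of those in the treatment group who go for a checkup with those in the control area who do not", and attenders in the two arms are not compared with each other. It concludes: "So, even if the service improves for those in the control barangay, it does not invalidate our identification strategy".

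The models are in Section 3.2. For 6.1: "Note that only individuals that are either in the lottery incentive group or in the control group are used for this regression". The regressor is the predicted value of "a binary variable that equals one for those who attended a RHU/CHC for a checkup". The first stage, 6.2, is fitted "Using both the treated respondents who are offered the lottery prize and the control respondents who are not". Section 10.1 (Compliance rate) expects some controls to attend without any inducement, and the elaboration of H6c calls such people always takers. Section 5.3 gives the aim as the effectiveness of the programme as it currently runs. The working hypothesis, H6a, is: "As currently implemented, PhilPEN does not reduce the risk factor exposure and increase the medication of individuals with elevated CVD risk".

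The ticket condition appears in several parts of Section 5.3, in Section 10.2 and in the appendix instructions to the point person. The wording is not the same throughout.

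**The concern.** The reassurance in Section 10.2 would follow if control attenders played no part in the estimate. They do play a part. If they receive a different service from voucher holders, the offer affects outcomes through the quality of care as well as through attendance. The instrument then no longer isolates the effect of attending.

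The lottery contrast serves the study's second objective and uses 2 x 1,361 = 2,722 of the 3,021 planned follow-up respondents (90%). If extra care is beneficial, the distortion is towards benefit. A null result, as H6a expects, could not be explained by it. A positive result could be, in part. The outcomes closest to the visit are most exposed: advice (xii to xviii), undiagnosed hypertension (x) and medication (xi). The Globorisk score moves only through blood pressure, BMI and smoking, so it may shift less.

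**Working it through.** **1. The plan's own figure.** Inputs (Sections 10.1 and 10.2): 5% significance (taken as two-sided), 80% power, means 11.35 and 10.89, SD 11.35/5 = 2.27, ICC 0.1, 10 per cluster, autocorrelation 0.6, compliance 0.6.

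n = 2 x (1.960 + 0.842)² x (2.27/0.46)² x (1 - 0.36) x (1 + 9 x 0.1) = 464.8, so 47 clusters or 470 people. Then 470/0.6² = 1,306, as in Table 6. Dividing by compliance squared is sizing for a whole-arm comparison, so the power section also assumes the contrast of models 6.1 and 6.2.

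**2. What 6.1 and 6.2 estimate.** Covariates aside, the estimate is the arm difference in outcome divided by the arm difference in attendance. Let a be attendance in controls and a + k attendance in the lottery arm. Write effects as benefits: T for a usual visit, T + g for a voucher holder, T - d for any other attender.

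- Equal improvement e for all attenders: [(a + k)(T + e) - a(T + e)]/k = T + e. This holds for any a. The instrument stays valid, but the quantity is the effect of the improved service.
- Differential care: [(a + k)(T + g) - a(T - d)]/k = T + g + (a/k)(g + d).

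The term g means that compliers received a different version of the visit. The term (a/k)(g + d) comes from always takers being treated differently in the two arms. Their usual effect cancels between arms, so it need not equal T; using the same g for them as for compliers is a simplification.

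**3. The contrast described in Section 10.2 is a different quantity.** Assume outcome means without treatment of -0.2, 0 and +0.2 SD for always takers, compliers and never takers, with a = 0.2, k = 0.6 and no effect of attending.

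- Lottery attenders: (0.2 x -0.2 + 0.6 x 0)/0.8 = -0.05 SD.
- Control non-attenders: (0.6 x 0 + 0.2 x 0.2)/0.8 = +0.05 SD.
- That contrast gives -0.10 SD; the instrumental variable estimate gives 0.

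**4. Size.** The values of a, g and d are assumptions. Section 10.1 gives a compliance rate of 0.6 (0.5 in sensitivity analysis), taken here as k.

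| Assumed care difference | k | a = 0 | a = 0.1 | a = 0.2 | a = 0.4 |
|---|---|---|---|---|---|
| g = d = 0.25T | 0.6 | 1.25T | 1.33T | 1.42T | 1.58T |
| g = d = 0.25T | 0.5 | 1.25T | 1.35T | 1.45T | 1.65T |
| g = 0, d = 0.25T | 0.6 | 1.00T | 1.04T | 1.08T | 1.17T |

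With k = 0.6, a = 0.4 means that the whole lottery arm attends, so it is a ceiling.

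Against the 0.2 SD target, take a total difference g + d of 0.1 SD and a from 0.05 to 0.2, so that a/k runs from 0.05/0.6 = 0.083 to 0.2/0.5 = 0.40.

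- All neglect (g = 0): the shift is 0.008 to 0.04 SD, or 4 to 20% of the target.
- All extra care (d = 0): it is 0.1 + 0.008 to 0.1 + 0.04 = 0.108 to 0.14 SD, or 54 to 70% of the target, measured from usual care.

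The direct term g therefore dominates unless the difference is mostly neglect.

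**5. The ticket condition, side by side.**

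- Section 5.3, opening: respondents are told to go for a checkup; facilities are told to make whatever assessment they think fits the patient.
- Section 5.3, Voucher contents: a physical assessment.
- Section 5.3, Instructions to the point person: assess claimants like any other attender; the ticket follows any assessment thought suitable.
- Section 10.2: a completed physical assessment.
- Appendix instructions, items a and c: the ticket is released once the recommended procedures or examinations are complete, and is refused to a confirmed holder who declines them.

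The appendix goes further than the voucher text, the instruction to treat claimants like other attenders, and Section 10.2. It goes only somewhat further than the other two formulations in Section 5.3. Rewarding completion is itself a way in which voucher holders could receive more than usual attenders.

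**6. Recording of attendance.** The model's variable is attendance for a checkup. Section 5.3 tracks voucher holders through ticket claims, which cannot exist for controls. No passage says how a holder who attends but declines is coded.

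**The case against.** The best defence is that this is loose wording, with no design flaw behind it. Section 3.2 states the estimator and the complier estimand correctly and names always takers. The closing sentence of Section 10.2, read literally, concerns improved service in control barangays, and for an equal improvement it is right. Facilities are asked to act as usual in Sections 5.3 and 10.2, which should keep g and d small. Excluding people already on antihypertensives may keep a low. All of this stands. What remains is that the section raises differential care itself and answers it with operational requests only.

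A reader might infer that the study will actually compare lottery attenders with control non-attenders and so build in selection bias. The documents do not support that: 6.1 and 6.2 are the stated analysis. Nor do they support reading the appendix as contradicting the whole main text, since parts of Section 5.3 already tie the ticket to an assessment judged suitable. The pages just before those instructions were not available, so what the recommended procedures cover, and how often the condition would bind, cannot be checked. Finally, attenders who decline are not lost from view: item c has the reason noted, and item 7 returns the records to the study team. What is missing is the coding rule and a source common to both arms.

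**Conclusion.** The concern holds in a limited form. The reasoning in Section 10.2 does not describe the planned estimator and gives no protection if voucher holders receive more care than other attenders. The estimate is then T + g + (a/k)(g + d), and a positive lottery result cannot be attributed to PhilPEN as usually delivered. A null result is not undermined when the extra care is beneficial.

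The algebra is firm; the size is not known. Every percentage above rests on assumed attendance and care differences. It would be tempting to quote 4 to 20% of the target as the bias, but that range omits g and is the departure from usual care only when the whole difference is neglect. Models 6.1 and 6.2 and the sample size need no change. The ticket point is less certain than the estimator point because part of the appendix could not be seen.

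**What to change.** 1. Replace the argument in Section 10.2 with the actual condition: two-stage least squares compares whole arms, and it needs voucher and non-voucher attenders to receive the same service. Say that an equal improvement keeps the instrument valid but changes what is measured. Limit the interpretation of a positive result accordingly.
2. Reconcile the ticket condition across Section 5.3, Section 10.2 and the appendix instructions. Define s_i as attendance reported in the survey, asked identically in both arms, so that a holder who attends but declines a procedure counts as attending. Keep ticket claims for running the draw. Confirm that the shorter follow-up questionnaire carries the attendance item.
3. Extend the monitoring already planned in Section 7 to a table, by arm, of advice and tests received among attenders, from the same survey items. The procedure notes under item d of the appendix instructions exist only for voucher holders and cannot serve. Label the table descriptive, because attenders select themselves, and imprecise. With a from 0.05 to 0.2 there would be 68 to 272 control attenders (1,361 x a) against 749 to 1,089 in the lottery arm (1,361 x 0.55 to 0.80). At a proportion of 0.5 and ICC 0.1, ignoring clustering by facility, the 95% half-width is about 13 to 7 percentage points.

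The cost is one rewritten paragraph, aligned ticket wording, one sentence defining attendance and one table. I would not add a regression of control outcomes on how many lottery barangays share the facility. With 1,361/63 = about 22 controls per facility it has little power, and using controls alone it cannot detect extra attention to voucher holders.
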